# **REVISION HISTORY**

Revision #	Version Date	Summary of Changes	Consent Change?
#1	11/28/17	Added weight measurement at Follow-Up visits	YES
# 2	5/16/18	Adding functional magnetic resonance imaging (fMRI)	YES
	_		

## ABBREVIATIONS/DEFINITIONS

- tDCS transcranial direct current stimulation
- fMRI functional magnetic resonance imaging
- FC functional connectivity
- NAcc nucleus accumbens
- DLPFC dorsolateral prefrontal cortex
- MNWS Minnesota Nicotine Withdrawal Scale
- QSU Questionnaire of Smoking Urges
- CO carbon monoxide

# STUDY SUMMARY

Study Title	Effect of a Non-Invasive Brain Stimulation Technique on Smoking Cessation Behaviors	
Study Design	Randomized Double-Blind Pilot Study	
Primary Objective	To determine the feasibility of using tDCS (a non-	
	invasive brain stimulation technique) as a treatment	
	for smoking cessation	
Research	Transcranial direct current stimulation (tDCS)	
Intervention(s)/Investigational		
Agents		
IND/IDE # (if applicable)	n/a	
Investigational Drug Services	n/a	
# (if applicable)		
Study Population	medically stable smokers	
Sample Size (number of	20 to complete the study	
participants)		
Study Duration for Individual	Approximately 6 weeks	
Participants		

## 1.0 Objectives

1.1 Aim 1: To determine the feasibility of using transcranial Direct Current Stimulation (tDCS) in a population of smokers interested in cessation

#### 2.0 Background

- 2.1 Significance of Research Question/Purpose: The morbidity and mortality associated with smoking is well characterized, with the most recent Surgeon General's report estimating that approximately 480,000 deaths annually in the United States are attributable to smoking. Although 70% of smokers indicate a desire to quit, the best current treatments result in less than 30% achieving long-term abstinence. New treatments for tobacco dependence are introduced rarely with only three medications currently approved for increasing smoking cessation rates (i.e. medicinal nicotine, varenicline, bupropion). Clearly, additional therapies are needed
- 2.2 Preliminary / Existing Data: Transcranial direct current stimulation (tDCS) is a non-invasive brain stimulation technique in which a weak electrical current (2mA or less) is applied to the scalp via anodal and cathodal electrode sponges, causing either increases or decreases in cortical excitability, respectively. Use of this technology has been studied for the treatment of several disorders (e.g. depression, Alzheimer's disease, Parkinson's disease) and has been suggested as a potential treatment modality for addiction. Drs. [name] and [name] have identified, using functional magnetic resonance imaging (fMRI), brain biomarkers that support long-term abstinence from alcohol in those with alcohol use disorder. Specifically, cross-sectional and longitudinal findings suggest that higher functional connectivity (FC) between the nucleus accumbens (NAcc) and dorsolateral prefrontal cortex (DLPFC) is a potential brain biomarker that is associated with abstinence. Long-term abstinent alcoholics (7 years of abstinence) have higher resting FC between NAcc and DLPFC when compared to nonsubstance abusing healthy controls. Short-term abstinent alcoholics (11 weeks of abstinence) have intermediate FC (lower than long-term abstinent alcoholics and higher than controls). Further, lower FC between NAcc and DLPFC at 11 weeks of abstinence can be a predictor of subsequent relapse (with 74% accuracy). Moreover, in a pilot longitudinal study examining resting FC of NAcc at 5 and 13 weeks of abstinence in individuals with substance use disorder, FC between NAcc and DLPFC decreased from 5 to 13 weeks of abstinence in subsequent relapsers, while it increased in subsequent abstainers. One interpretation of this data is that long-term abstinence is supported by a compensatory mechanism that mediates proper executive function over reward (which is mediated by DLPFC-NAcc FC). This information provides a potential brain marker that could be an intervention target if methods can be identified that increase FC between DLPFC and NAcc.

Cognitive flexibility, the ability to change maladaptive behavior, depends on DLPFC input to NAcc.  DLPFC transmits reward representations to NAcc through glutamatergic projections that guide goal-directed behavior.  If DLPFC

fails to activate when required, as often observed in substance use disorder, target neurons in the NAcc core do not receive critical information needed to select the appropriate outcome, causing acquired maladaptive response patterns to persist (e.g. drug consumption). Higher FC between DLPFC and NAcc may be achieved by stimulating DLPFC while subjects perform tasks that require cognitive flexibility, an aspect of executive functioning.

Transcranial direct current stimulation (tDCS) has shown in both healthy subjects and in patients (e.g. Parkinson's disease, stroke, and depression) to modulate synaptic strengthening and neurotransmitter-dependent plasticity underlying changes in behavior and learning. It therefore has the potential to increase functional connectivity between NAcc and DLPFC when paired with a cognitive task engaging this pathway. As previously described, strengthening this pathway should facilitate proper selection of goal-directed behavior and decrease craving in those with substance use disorder.

There is currently limited data regarding the efficacy of tDCS on smoking cessation and no data regarding the efficacy of combining tDCS with a concurrent task requiring cognitive flexibility. Although studies have assessed the effect of tDCS on smoking behavior, these have not combined stimulation with a task requiring cognitive flexibility nor have these studies assessed cessation outcomes. Instead, smoking cues were presented either immediately prior to, during or immediately after neurostimulation with the outcomes assessed being either cue induced craving severity, number of cigarettes smoked during the days of stimulation or using laboratory based smoking choice paradigms. These studies have generally found small but positive effects in these measures. However by not combining tDCS with the cognitive flexibility task, these studies may not have been able to maximize the effects of this intervention.

## 3.0 Study Endpoints/Events/Outcomes

- **3.1** Primary Endpoint/Event/Outcome: As a pilot study, the main objective of this investigation is to determine the feasibility of using the proposed approach as a method by which to increase smoking cessation rates. The primary endpoint is therefore to determine if recruiting smokers into a study evaluating tDCS will be feasible and if the intervention is well tolerated by smokers.
- 3.2 Secondary Endpoint(s)/Event(s)/Outcome(s): Secondary endpoints include measures associated with smoking cessation outcomes including time to smoking lapse, time to smoking relapse, number of cigarette smoked, severity of craving and severity of withdrawal symptom score. We will also assess impulsivity as tDCS may impact this measure. fMRI measures will be assessed in the subpopulation of subjects enrolled after protocol revision # 3 is approved and after all preparations to enroll subjects into this portion of the study are complete.

# 4.0 Study Intervention(s)/Investigational Agent(s)

**4.1** Description: The tDCS will be performed with the Neuroelectrics Starstim NE (Neuroelectrics Barcelona, Spain). This device is located in the MnDRIVE Non-invasive Neuromodulation Laboratory (Room 247 at the Delaware Clinical

Research Unit of the CTSI).

- **4.2** Drug/Device Handling: To minimize risks of tDCS, study staff will be trained in and use standards of administration that have been shown as safe in numerous other studies using transcranial direct current stimulation. A recent review of the safety of tDCS found no reports of serious adverse effects or irreversible injury across over 33,200 session and 1,000 subjects with repeated sessions. The length of administration of the current, size of electrode sponges used, and method of applying stimulation are no higher than those that have been demonstrated as safe.
- **4.3** IND/IDE. In studies using tDCS, approval of the device in research has generally been granted without an investigational device exemption due to meeting criteria for non-significant risk (NSR). A recent review of regulatory considerations for the clinical and research use of tDCS concluded that in the United States, "IRB's ubiquitously (at a minimum overwhelmingly) designate tDCS trials NSR (see adverse event discussion above), thus not requiring a formal IDE application to the FDA." 
- **4.4** Biosafety: N/A

#### 5.0 Procedures Involved

- **5.1** Study Design: This study is a randomized double-blind pilot study in which subjects will receive either active or sham tDCS
- **5.2** Study Procedures: The following procedures will occur during the study
- 5.2.1 Screening visit: Initial eligibility will be assessed via a phone interview. Those likely to qualify will be scheduled for a screening visit at which written informed consent will be obtained and eligibility confirmed. Medical, psychiatric and smoking history will be obtained via subject report with smoking status biochemically confirmed (via an exhaled carbon monoxide (CO) concentration of > 8 ppm or a urinary nicotine test strip = 6). Baseline levels of a variety of measures such as severity of smoking urges, severity of withdrawal symptoms, extent of nicotine dependence and how subjects evaluate their current cigarettes will be assessed via questionnaires. Height and weight will be measured. Those who qualify will be scheduled for a week during which they will come in daily for 5 consecutive days to receive tDCS treatments (active or sham) and will be asked to maintain a daily tobacco use diary in order to assess baseline levels of smoking. Subjects enrolled after revision # 3 has been approved and all preparations to enroll subjects into the scanning portion of the study are complete will be asked to come in for two additional visits to collect fMRI data: one visit before tDCS treatments begin, and a second visit after all tDCS treatments are completed.
- 5.2.2 MRI scanning visits (2 visits, 1 visit occurring during the week prior to and the other visit occurring during the week following the tDCS visits): Participants will undergo an MRI scan (3T), which takes about 75 to 80 minutes. MRI involves taking pictures of the participant's brain, from which the properties of certain brain tissues can be measured. These scans are strictly for research

purposes and therefore will not receive a clinical or medical interpretation. For the scan, the participant will be asked to lie down quietly on a bed, and the bed will slide into the scanner. Once the participant is inside the scanner, the imaging will begin. During the scan, the participant will be asked to lie quietly in the scanner with their eyes closed and may also be asked to perform a cognitive task (e.g., reversal learning task). The MRI scan will be performed at the University of Minnesota's Center for Magnet Resonance Research.

5.2.3 tDCS Visits (5 visits on consecutive days): At each of these visits, subjects will receive active or sham tDCS. The length of stimulation and the current used is consistent with the parameters previously found in clinical studies of alcohol dependence to reduce relapse.  Specifically, subjects will receive two 13 minute 2-mA sessions to the left DLPFC at each visit with a rest interval (no stimulation) of 20 minutes in between.  While receiving stimulation, subjects will perform cognitive training tasks drawn from the commercially-available Brain HO suite of tasks. Over each 46 minute period (i.e., the two 13 minute tDCS session separated by 20 minutes in between), each of 7 tasks will be performed for approximately 6 minutes. These tasks are designed to be adaptive based on participants' performance and therefore are more engaging than non-adaptive tasks. Multiple peer-reviewed medical and science journal articles have been published on Brain HQ exercises and assessments in varied clinical populations. Its commercial availability also makes Brain HQ amenable to potential future large scale deployment. Table 1 summarizes the Brain HQ tasks that will be utilized

Table 1: Brain HQ Ex	ecutive Functio	n Tasks	
Task	Modality	Domain	Description
Freeze Frame	Visual	Behavioral Inhibition	Must decide if pictures match one presented at start of task. Respond ONLY when pictures DO NOT match.
Mixed Signals	Visual & Auditory	Behavioral inhibition	Listen to a number, letter of color while looking at a set of numbers letters or colors. Decide if the two stimuli match quickly as possible.
Divided Attention	Visual	Behavioral inhibition; Set shifting	Decide if two objects match depending on rule (color vs. shape).
Mind Bender	Visual	Set shifting	Must respond based on two competing rules depending on the type of stimuli
Card Shark	Visual	Working Memory	Visual n-Back
Auditory Ace	Auditory	Working Memory	Auditory n-back task
Juggle Factor	Visual	Working Memory	Presented with a sequence of numbers that are placed within moving circles; Must reconstruct the sequence in the right order & locations.

At the beginning of each tDCS visit, participants will be assessed for number of cigarettes smoked 24 hours prior to the session, the time since last cigarette and exhaled CO levels. A cigarette evaluation scale will be completed at each visit. Additionally, adverse events, smoking urges and nicotine withdrawal symptom severity will be assessed before and after each session using several questionnaires. At the first tDCS session, urine will be collected to be analyzed at a later time for markers of cigarette smoking (e.g., cotinine concentrations). Prior to the first and after the last tDCS session, participants will also complete an impulsiveness questionnaire as this parameter is thought to be affected by tDCS, a

questionnaire assessing nicotine dependence as well as a questionnaire assessing motivation and self-efficacy to quit smoking.  Total participation time at each visit is not expected to exceed 2 hours per day.

At these visits, participants will be provided a smoking cessation treatment manual (Clearing the Air) and begin preparation for the quit date, which will be at the end of the 5th visit. The standardized content of the brief (10 min) behavioral treatment session provided to participants will include discussing benefits of quitting, ways to prepare the environment to minimize smoking cues (e.g., removing ashtrays), and methods to reduce craving and withdrawal symptoms (e.g., deep breathing). Participants will also keep track of situations associated with smoking and begin to develop a plan to deal with these situations.

This tDCS device to be used in this study is located in the MnDRIVE Non-invasive Neuromodulation Laboratory. There is currently no evidence of serious side-effects.  Mild side-effects that typically resolve upon discontinuing tDC include light itching under the electrode at the beginning of administration, headache, fatigue, and nausea. The subject may choose to discontinue stimulation at any time during the session if experiencing excessive discomfort or side effects. Although seizures are not a known risk of tDCS intervention,  anyone with a history or a risk for seizures will be excluded from the study. No other risks related to tDCS are anticipated.

- 5.2.4 Post Cessation Visits (4 visits): Follow-up visits will occur at each of 4 weekly visits. At each visit, smoking diaries will be collected and exhaled CO will be measured. Urine will be collected at the week 1, 2 and 4 visits. Weight will be measured at week 1, 2, 3 and 4 visits. Questionnaire assessing craving and withdrawal symptoms severity will be assessed as will the effects that participants report from smoking (via the cigarette evaluation scale).
- **5.3** Individually Identifiable Health Information: All information is collected directly from subjects (i.e., medical records will not be requested) and this is not a treatment study. The data being collected therefore does not meet the definition of PHI.
- **5.4** Use of radiation: N/A
- **5.5** Use of Center for Magnetic Resonance Research: This study has been reviewed by the CMRR (Project Application Review System application # 5101)

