## 16.0 Data Management

Data Analysis Plan: Data collected in this pilot study will be used as preliminary data and proof of concept to facilitate the design of and estimate power for subsequent larger grants. Descriptive statistics will conducted and effect sizes will be estimated. Linear mixed models will be used to examine time, group (sham vs. active) and group by time effects for various continuous outcome measures (e.g. craving). Survival analyses will be used to examine group differences on time to relapse to smoking.

- **16.1** Power Analysis: As this is a pilot study, no power analysis was done.
- **16.2** Data Integrity: In order to ensure that data entry is correct, data collected on paper questionnaires will be entered twice with the two entries compared and any discrepancies resolved.

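### Does section 5.2.3 contradict itself by placing the cognitive tasks under stimulation while its timings put part of them in the interval without current?

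*Combined protocol and SAP*

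**What the plan says.** Section 5.2.3 (tDCS Visits) gives each visit "two 13 minute 2-mA sessions to the left DLPFC at each visit with a rest interval (no stimulation) of 20 minutes in between". On the timing of the cognitive training it has two adjacent sentences. The first reads "While receiving stimulation, subjects will perform cognitive training tasks". The second sets the time frame, "Over each 46 minute period (i.e., the two 13 minute tDCS session separated by 20 minutes in between", and says that within it "each of 7 tasks will be performed for approximately 6 minutes".

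Section 2.2 supplies the rationale. Of tDCS it says "It therefore has the potential to increase functional connectivity between NAcc and DLPFC when paired with a cognitive task engaging this pathway", and it describes the existing literature as offering "no data regarding the efficacy of combining tDCS with a concurrent task requiring cognitive flexibility".

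Two other places show what depends on this. Section 3.1 makes the primary endpoint to "determine if recruiting smokers into a study evaluating tDCS will be feasible and if the intervention is well tolerated by smokers". Section 16.0 says the data will be "used as preliminary data and proof of concept to facilitate the design of and estimate power for subsequent larger grants".

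**The concern.** Read alone, the first sentence suggests that the training takes place under current. The second sentence makes that impossible for all of it, because the tasks need more minutes than the two sessions provide and the period includes a 20-minute interval labelled as rest. The protocol does not say in so many words that tasks continue through the interval, nor in what order they come.

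Pairing stimulation with a task is the study's stated idea, so this could matter in two ways. Staff might pause the tasks during the interval or run through it, which are different procedures. And someone planning a larger study from these effect sizes might believe that all the training was concurrent with stimulation when a sizeable part was not.

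**Working it through.** **Inputs, all from section 5.2.3:** two sessions of 13 min; one interval of 20 min without current; seven tasks of about 6 min each; a stated period of 46 min; five visits.

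**The plan's own figure.** 13 + 20 + 13 = 46 min, which matches.

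**Session time and task time.** Session minutes: 2 × 13 = 26. Task minutes: 7 × 6 = 42.

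**Task minutes outside the session windows.**
- Least, when every session minute carries a task: 42 − 26 = 16, and 16/42 = 38.1%.
- Most, when the interval is filled with tasks: 20, and 20/42 = 47.6%.
- Over five visits: 5 × 16 = 80 to 5 × 20 = 100, of 5 × 42 = 210.

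Both ends can occur. The session windows run from 0 to 13 and from 33 to 46 min. Task starts at 0, 6, 12, 18, 24, 30, 36 give overlaps with the windows of 6 + 6 + 1 + 0 + 0 + 3 + 6 = 22 min, leaving 20 outside. Starts at 0, 6, 12, 22, 28, 34, 40 give 6 + 6 + 1 + 0 + 1 + 6 + 6 = 26 min, leaving 16 outside.

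**Session minutes that carry a task.** This is the quantity the first sentence speaks to. Least: 42 − 20 = 22, and 22/26 = 85%. Most: 26 of 26.

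**Sensitivity.** The text says about 6 minutes, so the task length L is varied as an assumption. Outside minutes run from 7L − 26 to 20; session minutes with a task run from 7L − 20 to 26.

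| L (min) | Task min, 7L | Outside the windows | Share of task time | Session min with a task |
|---|---|---|---|---|
| 5 | 35 | 9 to 20 | 26% to 57% | 15 to 26 (58% to 100%) |
| 5.5 | 38.5 | 12.5 to 20 | 32% to 52% | 18.5 to 26 (71% to 100%) |
| 6 | 42 | 16 to 20 | 38% to 48% | 22 to 26 (85% to 100%) |
| 6.5 | 45.5 | 19.5 to 20 | 43% to 44% | 25.5 to 26 (98% to 100%) |
| 46/7 = 6.57 | 46 | 20 | 43% | 26 (100%) |

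**Could all the training fit under current?** Only at 26/7 = 3.7 min per task, well short of the stated 6. So the stated timings already imply that tasks run into the interval.

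**Tasks wholly inside the windows.** 26/6 = 4.3, so at most 4 of the 7 at 6 min per task. Nothing firmer follows. A claim that at least one task gets no current would need each task to be a single unbroken block, which the text does not say. If tasks may be split across the two sessions, all seven can receive some current.

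**Do the two sentences conflict?** The first says what happens during stimulation. It would be false if stimulation ran without tasks; it is not false if tasks also run at other times. The second says the tasks are spread over the whole period. Both hold if training continues through the interval, with rest meaning rest from current. In section 2.2, the first passage quoted describes a possible effect of the pairing and the second a gap in earlier studies; neither says that every training minute is under current.

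**The case for a change.** The best case for acting is that concurrency is the point of the study. Section 2.2 faults earlier work for not combining stimulation with a cognitive flexibility task. Table 1 labels only two of the seven tasks as set shifting (Divided Attention and Mind Bender), and with no order given these could fall in the interval. Section 5.2.3 is the only procedural account of task timing, a sentence or two would settle it, and later planners would know how much training was concurrent.

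Part of this stands. The first sentence is looser than it could be, the task order is not given, and a brief clarification would do no harm.

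It does not amount to a needed change. The risk that staff pause the tasks is limited by the text itself, since pausing is incompatible with about 6 minutes for each of seven tasks. The task schedule is described once, for both arms, so it cannot produce a difference between active and sham. The analyses in section 16.0 (descriptive statistics, effect sizes, mixed models for group and time, survival analysis of relapse) do not use task timing. The effect sizes describe stimulation and training as delivered. A descriptive timing summary would not separate concurrent from non-concurrent training, because participants are not randomised to different timings.

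**Conclusion.** The concern does not hold as an inconsistency. It is a clarity point in two adjacent sentences that are compatible, and the second discloses what the first leaves out. At 6 minutes per task, 16 to 20 of 42 task minutes per visit lie outside the session windows, while at least 22 of the 26 session minutes carry a task. Recruitment feasibility and tolerability, the randomised comparison and the planned analyses are the same whether or not the sentence is tightened.

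This rests on taking the stated timings at face value, with about 6 minutes read as 6 (the table shows 5 to 6.57), and on training continuing into the interval, which those timings imply. The minutes are minutes of current for the active arm only; for sham they are scheduled session time. Nothing here is a judgement on the stimulation parameters or on the task schedule.

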# 11.0 Local Number of Participants

11.1 Local Number of Participants to be Consented: We plan on recruiting subjects until approximately 20 have completed the study. We expect that as many as 50 subjects will undergo the consent process. Some of those that attend the screening visit will likely not meet inclusion / exclusion criteria whereas others will not be interested in participating.

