#### 13.0 Withdrawal of Participants

- 13.1 Withdrawal Circumstances: Participants will be withdrawn from the study if they report any side effects of greater than moderate severity or that raise any safety concerns. Subjects may also be withdrawn from the study if they fail to follow study procedures (e.g., show up to scheduled study visits). Additionally, subjects will be told that participation is voluntary and that they may discontinue participation at any time for any reasons.
- 13.2 Withdrawal Procedures: Subjects who withdraw from the study after having received tDCS will be asked if they can be contacted by telephone to ascertain smoking status. We will attempt to contact subjects by telephone who do not show up to scheduled visit to ascertain if they wish to continue to participate in the study (and if not, why not) and to determine smoking status.

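### Adverse events are scheduled only at the five tDCS visits, so effects after visit 5 and the outcome of events that cause withdrawal have no planned collection in the protocol

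*Combined protocol and SAP*

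**What the plan says.** Section 3.1 makes tolerability in smokers part of the primary endpoint, alongside feasibility of recruitment.

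During treatment, section 5.2.3 states that "adverse events, smoking urges and nicotine withdrawal symptom severity will be assessed before and after each session". There are five visits on consecutive days, and at each of them "subjects will receive two 13 minute 2-mA sessions to the left DLPFC at each visit".

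After treatment, section 5.2.4 sets out four weekly visits with diaries, exhaled CO, urine at three of the four, weight at all four, and then: "Questionnaire assessing craving and withdrawal symptoms severity will be assessed as will the effects that participants report from smoking". Adverse events are not in that list. In the scanned subgroup there is also an MRI visit after treatment (5.2.2: "the other visit occurring during the week following the tDCS visits"), described as a scan with a possible cognitive task.

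On withdrawal, section 13.1 says: "Participants will be withdrawn from the study if they report any side effects of greater than moderate severity or that raise any safety concerns". Section 13.2 then describes two telephone contacts. People who withdraw after receiving tDCS are called, if they agree, about smoking status. People who miss a visit are called about whether they want to go on, why not if they do not, and smoking status.

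Section 18 leaves safety monitoring to the CTSI monitoring group under procedures that the protocol does not set out.

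**The concern.** Adverse-event questioning stops when stimulation stops, although participants are seen for about four more weeks. A trial that has tolerability in its primary endpoint will be expected to say whether side effects went away and whether any appeared later. It will also be expected to say how the events serious enough to end participation turned out.

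The last group matters most. Under section 11.1, "We plan on recruiting subjects until approximately 20 have completed the study". Someone withdrawn for a side effect does not count towards the 20 and is in effect replaced. These people are few but informative about tolerability, and the contact planned for them asks about smoking. Section 5.3 says that data come from the participants themselves and that medical records are not requested, so the protocol offers no second source for what is not asked.

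**Working it through.** The documents give no figure to reproduce: section 16.1 states that no power analysis was done. The check is a count of scheduled questions, contact by contact.

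| Contact | Section | Adverse events listed? | What is listed |
|---|---|---|---|
| tDCS visits 1 to 5 | 5.2.3 | Yes, before and after each session | also urges, withdrawal symptoms, CO, cigarettes smoked |
| Weekly visits 1 to 4 | 5.2.4 | No | diaries, CO, urine, weight, craving, withdrawal symptoms, cigarette evaluation |
| Post-treatment MRI (scanned subgroup) | 5.2.2 | No | scan, possible cognitive task |
| Call after withdrawal | 13.2 | No | smoking status, if the person agrees to be called |
| Call after a missed visit | 13.2 | No | wish to continue, reason if not, smoking status |

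**Coverage by visit.** From first stimulation there are 5 + 4 = 9 visits, and adverse events are listed at 5 of 9. In the scanned subgroup there are 5 + 4 + 1 = 10 visits, and they are listed at 5 of 10.

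**Number of checks.** If a session means the visit, 5 × 2 = 10. If it means each 13-minute stimulation, 5 × 2 × 2 = 20. The text allows either reading. Both end at visit 5.

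**Next-day persistence.** The pre-session checks at visits 2 to 5 look back on visits 1 to 4. For a participant who continues, 4 of the 5 treatment visits therefore have a next-day check. Visit 5 has none.

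**After the last check at visit 5.** No question is scheduled at the 4 weekly visits, or at the MRI visit where there is one. Four weekly visits make this about four weeks, out of a participation of about six weeks (section 8.0).

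**After withdrawal.** An event that begins during stimulation can still be met by that visit's post-session check, and an event that worsens over several days can be met by several checks before the person leaves. What is not scheduled is any question after the last check attended. The missed-visit call may reveal an event as the reason for stopping, but it is not set up to record severity, duration or resolution.

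**Is the list in 5.2.4 meant to be complete?** It names the weeks at which urine and weight are taken, and the revision history shows that weight at follow-up was added by a formal revision. Section 5.2.3 names adverse events where they are to be asked. It is reasonable to read 5.2.4 as the schedule and not as a selection from it.

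**The case against.** The strongest reply is that the primary endpoint asks whether the intervention is tolerated, and the intervention lasts five days, all of them actively covered. Section 14.1 describes mild effects that usually stop with the current, and most such effects would be caught in the treatment week. The weekly visits exist for the smoking outcomes. Participants can still mention a problem there, and the rule in 13.1 is not confined to the treatment week. The section 18 procedures might also include follow-up of adverse events. All of this stands, and it is why the point is small. It does not close the gap: spontaneous report is not scheduled collection, visit 5 has no next-day check, and the protocol text commits nobody to record how an event that caused withdrawal ended.

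Three stronger readings are tempting and are not supported.

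- A reader might infer that tolerability is not properly assessed. The 10 or 20 checks in the treatment week contradict that.
- A reader might infer that people withdrawn for side effects are never asked about them again. Same-visit post-session checks, and any checks earlier in the course of the event, contradict that.
- A reader might try to size the withdrawn group from section 11.1, where "We expect that as many as 50 subjects will undergo the consent process" against about 20 completers. That figure is an expectation and not a limit, and the section explains the difference by ineligibility and lack of interest. It says nothing about withdrawals for side effects.

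**Conclusion.** The gap is real in the protocol text and minor in weight. Scheduled adverse-event collection ends with the last check at visit 5. As written, the trial can describe tolerability during the stimulation week, including next-day persistence after four of the five visits. It cannot describe, from planned questions, (a) effects present or arising in the following four weeks or so, which concerns every participant who finishes treatment, or (b) the duration and resolution, after the last attended check, of events in people withdrawn under 13.1. The number of people in (b) is not given.

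Neither the share of events missed nor the size or direction of any bias can be estimated from the documents, and none is claimed. The conclusion assumes that the list in 5.2.4 is the full schedule. It concerns what the protocol says. What would be collected in practice also depends on case report forms and monitoring procedures that the documents do not show.

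**What to change.** 1. In 5.2.4, add the adverse-event questions used at the tDCS visits to the weekly visits. Week 1 is the priority, because it is the first scheduled weekly visit after the last stimulation.
2. In 13.2, add adverse events, their severity and their resolution to both contacts: the call to those who withdraw after tDCS and the call after a missed visit.
3. In section 16.0, state that adverse events will be reported by arm for everyone who received any stimulation, not only the completers. Show the treatment week and follow-up separately, and read follow-up events alongside the withdrawal score and smoking status.

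If follow-up adverse events are already collected under the section 18 procedures, a sentence in 5.2.4 saying so would settle item 1. Item 2 would still need its own wording.

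The cost is low: a few questions at visits and calls that already take place. Section 5.2.3 mentions several questionnaires and names no adverse-event form, so the wording may need adapting to a week's recall and to the telephone. The revision that added weight at follow-up changed the consent form, and this one might too.

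The main drawback is attribution. Participants "begin preparation for the quit date, which will be at the end of the 5th visit", so the weekly visits all fall after the quit date. Nicotine-withdrawal complaints may be recorded as adverse events, possibly more often in the arm with more abstinence. Separate reporting limits this without removing it, and with about 20 completers attribution will be weak. People who decline to be called will still be missed.
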